Note: Complications caused by concomitant treatments not imposed by the clinical investigation plan are considered not related. Similarly, several routine diagnostic or patient management procedures are applied to patients regardless of the clinical investigation plan. If routine procedures are not imposed by the clinical investigation plan, complications caused by them are also considered not related.

Intensity of Symptoms

Mild:

The subject is aware of the sign or symptom, but finds it easily tolerated. The event is of little concern to the subject and/or little clinical significance. The event is not expected to have any effect on the subject's overall health or well-being.

Moderate:

The subject has discomfort enough to cause interference with or a change in usual activities. The event is of some concern to the subject's health or well-being and may require medical intervention and/or close follow-up.

Severe:

The event interferes considerable with the subject's usual activities. The event is of definite concern to the subject and/or poses substantial risk to the subject's health or well-being. The event is likely to require medical intervention and/or close follow-up and may be incapacitating or life threatening. Hospitalization and treatment may be required.

Note: The term "severe" refers to the intensity of the event and can be used with any event, without regard to whether or not it meets the criteria for being classified as "serious" or "unanticipated". For example, a subject can have a severe headache, but it is not a serious event.

Outcome Definitions

The outcome is in relationship to the Adverse Event, not the treatment rendered for the event (if any).

Resolved:

The adverse event has been resolved and/or no further treatment is required to treat the reported condition or illness.

Tolerated:

The adverse event will most likely never be resolved. The subject “tolerates” the illness or condition as a matter of life.

Pending:

Treatment or diagnostic studies were prescribed for the adverse event and the outcome of the adverse event is not yet known.

Study Withdrawal:

Due to the adverse event, the subject was withdrawn from the study.

Device Removal:

The adverse event resulted in the removal of a study device.

Reoperation of Affected Joint:

The adverse event resulted in reoperation of the study joint, but the reoperation did not include removal of a study device.

Death:

The outcome indicates the subject died as a direct result of the reported adverse event.

XIII. Monitoring

Prior to initiating the clinical study, the Sponsor may conduct a site evaluation visit to ensure the Investigator(s) and study staff understands the study protocol and requirements and have adequate time and resources to implement and conduct the study. Prior to study initiation, the Investigator must have a fully executed CTA, IRB approval of the study protocol, and the study **Informed Consent**.

During the course of the study, the Sponsor will conduct periodic central monitoring and maintain contact with the study staff to monitor compliance and evidence of adverse events in accordance with the Sponsor's policies and procedures. The Sponsor will address any identified non-compliance with the executed CTA, study protocol, and applicable regulatory requirements.

If onsite monitoring visits are deemed appropriate by the Sponsor, the Investigator will permit representatives of the Sponsor's monitoring team to have direct access to inspect all source data/documents, study documents/binders, study subject case report forms, corresponding sections of study subject medical/hospital records, and any other documents relevant to the study. All Sponsor visits will be documented using the **Monitoring Visit Log**.

XIV. Risk Analysis

This PMCF is classified as minimal risk and there are no anticipated risks specific to study participation other than the potential loss of confidentiality. There are no experimental procedures in this study and participation in this study is not anticipated to affect the medical treatment of enrolled subjects.

When used in accordance with product labeling, the risks associated with the use of the FastFrame External Fixation System are similar to those of the historical standard, the XtraFix® External Fixation System by Zimmer, Inc., when used for the same clinical indication or purpose. These risks are either general surgical risks or risks associated with the subject procedure/study device; however, unanticipated adverse events can occur.

XV. Statistical Methods

General Statistical Methods

Statistical methodology will consist of summarizing collected data descriptively. Categorical data (i.e., gender or race) will be summarized using counts and percentages, and 95% CI, over the time periods of interest. Continuous data, such as age, will be summarized by using means, medians, standard deviation, minimum, maximum, and 95% CI over the time periods of interest. Implant survival will be summarized using a Kaplan-Meier method and presented with rates (as percentages) and confidence intervals.

Sample Size

Calculation of sample size is based on previously published literature involving longitudinal data collection on temporary external fixation. Assuming a power level of 80% and an alpha level of significance of 0.05 ($\alpha = 0.05$), calculations were performed in order to determine the sample size needed for study significance using the following hypothesis test:

The hypothesis will be tested by the exact binomial test:

$$H_0: E_1 - E_0 \leq -\delta E$$

$$H_a: E_1 - E_0 > -\delta E$$

where:

$E_0 = 95\%$, the expected success rate

E_1 = the success rate in the FastFrame System treatment group

$\delta E = 0.10$, non-inferiority margin

In addition, one-sided 95% exact confidence Interval (CI), lower limit of the success rate, will be calculated.

Based on the hypothesis test above, 60 subjects will provide approximately 80% power for the one-sided exact binomial test at 0.05 significant level. The sample size was calculated using SAS for Windows version 9.4.

It was determined that the complication rate of devices comparable to the FastFrame External Fixation System is approximately 5%. Utilizing this figure, the power, and alpha level of significance, a sample size total (without any subjects becoming lost to follow-up) of 60 was obtained. Finally, in order to maintain a sample size large enough for statistical significance an estimated, 90% subject return rate is assumed for the duration of the device exchange follow-up visits. These lost to follow-up patients increase the sample size requirements to 66 subjects (after rounding up).

Visit	Subjects remaining in the study
Baseline	66
Follow-Up	60

XVI. Quality Control & Quality Assurance

The study is conducted in accordance with the Declaration of Helsinki and the ISO 14155:2020 and Regulation (EU) 2017/745.

The Investigator will be required to permit representative(s) of the Sponsor's monitoring team to inspect all case report forms and corresponding sections of the study subjects office records and/or hospital original medical records. These audits will be done for quality assurance purposes, i.e. verifying adherence to the Clinical Investigation Plan and the completeness and accuracy of the data being entered on the case report forms.

The Clinical Investigation Plan will be provided to all participating study centers. The Investigators will be fully trained in the proper reporting and submission of trial data prior to patient enrolment. Completed case report forms will be reviewed before entering the data into a central database by the Sponsor.

The Clinical Study Manager is responsible for generating data queries for missing or unclear data if needed. It is the responsibility of the Clinical Study Manager to ensure data quality.

There are regular meetings between the Investigators and Zimmer Biomet Clinical Affairs staff. Written correspondence to all sites is used to inform the Investigators of routine study details and to update them on study status.

XVII. Suspension or Premature Termination of the Clinical Investigation

A description of the criteria and arrangements for suspension or premature termination of the whole clinical investigation, of the clinical investigation in one or more investigation sites, or for individual subjects. Include the following, as applicable:

- Criteria for access to and breaking the blinding/masking code in the case of suspension or premature termination of the clinical investigation.
- Requirements for subject follow-up.

XVIII. Vulnerable Populations

Patients that are within one or more vulnerable populations, including children, prisoners, pregnant women, and handicapped or mentally disabled persons, are to be excluded from this study.

XIX. Amendments to the Clinical Investigation Plan

All amendments shall be agreed with the Sponsor and Investigator(s) and be recorded with a justification for the amendment. Approval of the IRB that reviewed the original protocol must be obtained if required according to the corresponding regulations. In the case of an amendment to the protocol, the revision history will be documented in the document history.

XX. Publication Policy

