Inclusion/Exclusion criteria	
Inclusion Criteria:
 
 • Patient must be 18 years of age or older • Patient must have been treated with either Knee Spanning or Damage Control FastFrame External Fixation System according to the indications stated in this protocol* 
Exclusion Criteria:
 
 • Patient has an active or suspected infection • Conditions that limit the patient's ability and/or willingness to follow instructions during the healing process • Inadequate skin, bone, or neurovascular status • Patient is a prisoner • Patient is pregnant and/or breastfeeding • Patient is a known current alcohol and/or drug abuser in the opinion of the Investigator • Patient has a mental or neurologic condition that will not allow for proper informed consent and/or participation in follow-up program in the opinion of the Investigator 
*EEA Indications (a subset of the cleared US indications): The FastFrame External Fixation System – Knee Spanning Kit is indicated for use in treatment of long bone (distal femur, proximal tibia) fractures. Specifically, the system is intended for temporary stabilization of open or closed fractures about the knee, typically in the context of polytrauma or where open or alternative closed treatment is undesirable or otherwise contraindicated.
 
The FastFrame External Fixation System – Damage Control Kit is indicated for use in treatment of mid-shaft long bone (femur, tibia) fractures. Specifically, the system is intended for temporary stabilization of open or closed fractures of the femur and tibia, typically in the context of polytrauma or where open or alternative closed treatment is undesirable or otherwise contraindicated.

Study Design	Prospective enrollment, prospective follow-up, single cohort study
Clinical Phase	Postmarket
Sample Size	Considering a 95% device success rate (5% device related complications) and a 10% non-inferiority margin, 60 subjects with a follow-up are required. With an estimated lost to follow-up/subject withdrawal rate of 10%, 66 subjects will have to be enrolled.
Length of Study	3 years (2 years of enrollment plus follow-up until exchange with another device) A follow-up visit will be completed at the time of exchange from FastFrame System to another device. Typically, this exchange occurs 2 to 4 weeks after injury.

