The management of orthopaedic polytrauma patients has developed greatly since the 1970s, when patients were deemed incapable of undergoing surgery³. In recent years, the use of temporary stabilization of fractures has been used with the goal to decrease operative time³, blood loss³, and the “second hit” inflammatory response from definitive surgical fixation². External fixators, a type of device intended for temporary stabilization, are typically made up of a combination of a frame, clamps, pins, and bars that properly stabilize and support the injured limb¹. In order for this stabilization to occur, the fractured bones are adjusted to reduce the fracture and the bars are connected to maintain the reduction¹. Unlike typical external fixators, the FastFrame External Fixation frames are pre-assembled and are designed for simplicity in the operating room. Each kit includes clamp bodies, pins, and telescoping bars that allow for proper reduction and rigid external fixation. This study will document the clinical outcomes of

trauma patients who require the use of the FastFrame External Fixation System - Knee Spanning and Damage Control kits legally manufactured by Zimmer, Inc.

VI. Study Objectives

The objective of this observational, prospective study is to confirm safety and performance of the FastFrame External Fixation System and corresponding instrumentation. The endpoints are defined to include the following:

Primary Endpoints

- Frequency and incidence of device-related adverse events and device deficiencies before the FastFrame External Fixation System is exchanged by another device (i.e. plates, screws, etc.). Refer to Section XII for additional details related to adverse event classification and device deficiencies.

Examples of device-related adverse events and device deficiencies include:

- Pin breakage and/or loosening requiring surgical intervention (i.e. pin removal or exchange) before planned exchange of the complete frame by another device
- Frame component failure (i.e. loosening, breakage, etc.) leading to clinically unacceptable loss of stability requiring unplanned readjustment or replacement of the frame

Secondary Endpoints

- Adverse events that occur between application of the FastFrame External Fixation System and exchange with another device that do not fall within the primary endpoint. Refer to Section XII for additional details related to adverse event classification.

VII. Study Design and Endpoints

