All surgeries will take place following the standard, approved surgical technique. During the course of the surgery, a **Surgical Device** CRF must be completed documenting the part and lot numbers of the implants. The FDA cleared or other local government regulatory body approved instructions for use and surgical technique must be followed for this product. Please refer to the latest versions of these documents on the Zimmer Biomet website, contact your local Clinical Study Manager, or contact a Zimmer Biomet sales associate for additional details. The following operative data will be collected on the following CRFs:

- **Operative Record**
- **Surgical Device**
- **Protocol Deviation, if applicable**
- **Adverse Event Report, if applicable**
- **Physician Imaging Assessment**
- **Photographs of study device in two (2) planes (A/P and lateral)**

Photographs will be stored in the Subject Binder as part of their casebook. Please write the Subject Case ID Number, Subject Initials, and Date (YYYY-MM-DD) on the photographs. If an adverse event occurs, an **Adverse Event Report** CRF will also be completed. See Management of Incurrent Events for additional details. Reason(s) for study completion must be documented on the **Study Completion** CRF.

Post-Operative Follow-Up Procedure

Post-operative clinical assessment will be conducted at the device exchange follow-up visit after the procedure. The device exchange of a FastFrame External Fixation Kit typically occurs 2-4 weeks after surgery. The following

CRFs will be collected at the follow-up visit when the study device is removed from the subject:

- **Physician Follow-Up Assessment**
- **Protocol Deviation, if applicable**
- **Adverse Event Report, if applicable**
- **Physician Imaging Assessment, if required**
- **Photographs of study device in two (2) planes (A/P and lateral), if required**
- **Study Completion**

Subjects will be followed post-operatively until the FastFrame External Fixation Kit is exchanged with another device or unless the primary endpoint is reached prior. Unless the study is otherwise closed, data will continue to be collected until the subject completes the study per the protocol, voluntarily withdraws from the study, is withdrawn from the study by the Investigator, is lost to follow-up, undergoes revision to remove a study device (does not include device removal as part of standard treatment), or expires.

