- b. led to serious deterioration in the health of the subject, users or other persons as defined by one or more of the following:
 1. a life-threatening illness or injury, or
 2. a permanent impairment of a body structure or a body function, including chronic diseases, or
 3. in-patient or prolonged hospitalization, or
 4. medical or surgical intervention to prevent life-threatening illness or injury or permanent impairment to a body structure or a body function.
- c. led to fetal distress, fetal death or a congenital abnormality or birth defect including physical or mental impairment.

Note: Planned hospitalization for a pre-existing condition, or a procedure required by the protocol, without serious deterioration in health, is not considered a serious adverse event.

Adverse Device Effect (ADE):

An Adverse Device Effect is an adverse event related to the use of an investigational medical device.

Note 1: This definition includes adverse events resulting from insufficient or inadequate instructions for use, deployment, implantation, installation, or operation, or any malfunction of the medical device.

Note 2: This definition includes any event resulting from use error or from intentional misuse of the medical device.

Serious Adverse Device Effect (SADE):

A Serious Adverse Device Effect is an adverse device effect that has resulted in any of the consequences characteristic of a serious adverse event.

Unanticipated Adverse Device Effect (UADE)

An unanticipated adverse device effect is a serious adverse device effect which nature, incidence, severity, or outcome has not been identified in the current risk assessment.

Note 1: Anticipated serious adverse device effect is an effect, which by nature, incidence, severity or outcome has been identified in the risk assessment.

Device Deficiency

A Device Deficiency is defined as an inadequacy of a medical device with respect to its identity, quality, durability, reliability, usability, safety, or performance.

Note 1: Device Deficiencies include malfunctions, use errors, and inadequacy in the information supplied by the manufacturer including labeling.

Note 2: This definition includes device deficiencies related to the investigational medical device or the comparator.

It is important to document in the study also all device deficiencies that could have led to a medical occurrence, but did not lead to an adverse event.

Causality Assessment (Relation to Device)

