The relationship between the use of the medical device (including the medical - surgical procedure) and the occurrence of each adverse event shall be assessed and categorized.

During causality assessment activity, clinical judgement shall be used and the relevant documents, such as the Investigator's Brochure, the Clinical Investigation Plan, or the Risk Analysis Report shall be consulted, as all the foreseeable serious adverse events and the potential risks are listed and assessed there. The presence of confounding factors, such as concomitant medication/treatment, the natural history of the underlying disease, other concurrent illness or risk factors shall also be considered.

Each adverse event will be classified according to four different levels of causality:

- Not Related
- Possible
- Probable
- Causal Relationship (Definitely Related)

The sponsor and the investigators will use the following definitions to assess the relationship of the adverse event to the investigational device, the comparator or the investigation procedure.

Not Related:

Relationship to the device, comparator or procedures can be excluded when: the event has no temporal relationship with the use of the investigational device, or the procedures related to application of the investigational device.

Possible:

The relationship with the use of the investigational device or comparator, or the relationship with procedures, is weak but cannot be ruled out completely. Alternative causes are also possible (e.g. an underlying or concurrent illness/ clinical condition or/and an effect of another device, drug or treatment). Cases where relatedness cannot be assessed, or no information has been obtained should also be classified as possible.

Probable:

The relationship with the use of the investigational device or comparator, or the relationship with procedures, seems relevant and/or the event cannot be reasonably explained by another cause.

Causal Relationship (Definitely Related):

The serious adverse event is associated with the investigational device, comparator or with procedures beyond reasonable doubt.

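### Is the only hypothesis test unusable because success is tied to complications in the benchmark but the primary endpoint also includes device deficiencies?

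*Combined protocol and SAP*

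**What the plan says.** - **Benchmark.** The Sample Size row of the synopsis (section III) starts from "Considering a 95% device success rate (5% device related complications) and a 10% non-inferiority margin". Section XV, Sample Size, gives the origin of the figure: "It was determined that the complication rate of devices comparable to the FastFrame External Fixation System is approximately 5" per cent.
- **Test.** Section XV specifies a one-sided exact binomial test at 0.05, with an expected success rate of 95% and a margin of 0.10. The null success rate is therefore 85%. The tested quantity is described only as "the success rate in the FastFrame System treatment group".
- **Primary endpoint.** Sections III and VI give "Frequency and incidence of device-related adverse events and device deficiencies before the FastFrame External Fixation System is exchanged by another device". The two examples in section VI are a pin failure needing surgical intervention and a frame failure needing unplanned readjustment or replacement.
- **Deficiencies.** Section XII says that "Device Deficiencies include malfunctions, use errors, and inadequacy in the information supplied by the manufacturer including labeling", and asks sites to document "all device deficiencies that could have led to a medical occurrence, but did not lead to an adverse event". The Scores/Performance Assessments row of the synopsis lists the complication rate and the deficiency rate as separate items.
- **Causality.** Section XII states: "Each adverse event will be classified according to four different levels of causality". One level is Not Related. The other three are Possible, Probable and Causal Relationship.
- **Unit.** Sections III and XV size the study in subjects, and section VIII defines the primary analysis population as enrolled subjects. Section X follows each subject "until the FastFrame External Fixation Kit is exchanged with another device or unless the primary endpoint is reached prior". Section X also gives a bilateral subject one case ID per procedure, and section XI asks for separate forms per device.

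**The concern.** The test needs one yes-or-no outcome per subject, and the plan does not write that outcome down. Two readings are available. On the narrow one, failure is a device-related complication, which is how the 95% is explained. On the wide one, failure is anything in the primary endpoint, including a use error or a labelling inadequacy that harmed nobody. Setting the wide event set against a complications-only benchmark would compare unlike things.

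Two smaller choices are also open: which causality levels make an event device-related, and how a subject with two frames enters the count.

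The decision turns on few events. With 60 subjects, 4 failures pass and 5 fail, so at the cut-off one disputed subject decides the result. The sponsor or its designee analyses an unblinded single cohort, so a reader may fear that the definition will be settled once the events are known.

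**Working it through.** **Inputs.** From section XV: n = 60, null failure rate 1 − (0.95 − 0.10) = 0.15, expected failure rate 0.05, one-sided level 0.05. The documents give no deficiency rate and no frequency of bilateral subjects.

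**Step 1: reproduce the plan's figure.** Let X be the number of failures, with P(X ≤ c) = Σ C(60, x) p^x (1 − p)^(60 − x), summed over x = 0 to c.

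- At p = 0.15: P(X ≤ 4) = 0.0424 and P(X ≤ 5) = 0.0968, so at most 4 failures are allowed.
- At p = 0.05: P(X ≤ 4) = 0.820, which agrees with the stated power of approximately 80%.
- One-sided 95% exact lower limits: 56/60 gives 85.4% (pass) and 55/60 gives 83.3% (fail).
- The cut-off stays at 4 for every n from 59 to 67, so modest variation in follow-up does not move it.

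The arithmetic holds. What remains is definition.

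**Step 2: compare the two readings.** Let X_N be the number of subjects with a device-related complication, and X_W the number with a complication or a deficiency. Every subject in X_N is also in X_W, so X_W ≥ X_N. Hence X_W ≤ 4 implies X_N ≤ 4, and a pass on the wide reading is always a pass on the narrow one. Even if the reading were picked after the events were known, the study could not pass more often than the narrow rule does. That rule has a false-pass probability of at most 0.0424 when the true complication rate is 15% or more. The same nesting applies to causality: counting Possible as related adds failures and never removes them.

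**Step 3: cost of the wide reading.** With the bar left at 85%, the chance of passing at assumed true failure rates is as follows.

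| Assumed true failure rate | P(X ≤ 4), n = 60 |
|---|---|
| 5% (the plan's figure) | 0.820 |
| 6% | 0.709 |
| 7% | 0.588 |
| 8% | 0.470 |

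The loss is in the sponsor's own chance of success. Protection against a false pass is unchanged. Only the 5% row rests on the documents.

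**Step 4: causality.** Section XII defines an adverse device effect as one related to use of the device, and its scale has a single unrelated class. The natural default is that the other three levels count as related. This is also the stricter choice.

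**Step 5: unit.** The sample size, the analysis population and the follow-up rule are all in subjects. The case-ID and form rules govern identification and data entry. The natural collapse is one outcome per subject, with failure if any frame fails. If frames were nevertheless analysed as independent, with an assumed 10 bilateral pairs among 60 frames, the true level would be 0.050, 0.055 or 0.069 at within-pair correlations of 0.3, 0.5 or 1.0. That is a small effect of an analysis the plan does not call for.

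**The case for a change.** The strongest opposing case is that a test with a stated hypothesis, margin, level and power should also state its outcome. Calling the study descriptive does not answer this, because section XV says the hypothesis will be tested. The synopsis lists complications and deficiencies as separate rates, so the two terms are not plainly synonyms, and the pin and frame failures in section VI are offered only as examples. With 4 failures allowed and a 17% chance of exactly 4 at a true 5% rate, borderline data are not remote.

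Much of this stands. Success is not defined, the causality levels that count are not named, and no sentence says how a bilateral subject is collapsed. Three things limit its force:

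- The 17% is the chance of landing on the cut-off. It is not the chance that the definition reverses the result, which also depends on how many subjects have only a deficiency or only a Possible event. The documents give no way to compute that.
- The term complications is not defined either, and pin or frame failures needing intervention could fairly be called complications. The 5% may already cover them.
- Both event types are recorded whichever reading is used, so no information is lost and a reader can see both rates.

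**Conclusion.** The plan leaves a definition unwritten, but no rule or figure in it is shown to be wrong. The 60 subjects and the stated power reproduce at 82.0%, with an attained level of 0.0424. Testing complications against the complications benchmark and reporting deficiencies alongside is sound. Testing the full primary endpoint against the same 85% bar is stricter and cannot create a false pass. The unit is the subject, and the causality scale has an obvious default cut. Choosing between the two readings is for the sponsor, and an analyst can carry out either from the data collected.

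The conclusion assumes that the bar stays at 85%, that each subject counts once, and that the narrow event set lies inside the wide one. It would weaken if a pass on complications alone were reported as a pass on the full primary endpoint, but nothing in the plan proposes that. The size of any mismatch between the 5% and the endpoint cannot be found from the documents and may be nil.
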